11.4. Amendments to the protocol

Neither the investigator, nor the monitor, nor the promoter will modify this protocol without first obtaining the consent of the other parties. The modification must be documented in writing. Any change in the research activity, except those necessary to eliminate an immediate apparent risk to the volunteer, must be reviewed and approved by the Ethics Committee before implementation. The promoter must send the amendments to the protocol to the health authorities, and the modifications may require the review and approval of the Ethics Committee.

11.5. Investigator Acceptance

The researcher commitment is included, if needed, in the documentation submitted to the Ethics Committee.

12. STATISTICAL ANALYSES

The analysis of the results of this study will be approached from two perspectives. On the one hand, the modified intention-to-treat (MITT) population will be analyzed, which corresponds to all those subjects who have used the product at least once and for whom satisfaction data is available. On the other hand, a per-protocol analysis will be carried out in which all randomized subjects who have followed the study instructions until the end of the study will be included.

The clinical evaluation data may be analyzed as quantitative or qualitative variables. In the first case, the results will be expressed as mean \pm standard deviation, minimum and maximum. In the case of qualitative variables, the results will be expressed as frequency and percentage. For all the parameters to be measured (both clinical variables and responses to questionnaires) there will be a baseline measurement taken before the start of the protocol that will serve as a control measurement. The change in the main variable (degree of satisfaction) will be analyzed

using the paired Student's T test. The change in the secondary variables will be studied according to their nature (qualitative or quantitative variables) and applying the corresponding test in each case: Chi square, Student's T, ANOVA, Kruskal-Wallis or Mann-Whitney U. The impact of each variable on the main variable will be assessed, especially the impact of treatment, diagnosis, age and gender.

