7.2. Study development

When a subject meets all the inclusion criteria and none of the exclusion criteria and has signed the informed consent document, he/she is electable to enter the study. The researchers will collect the data of each volunteer and notify Prospera Biotech of their inclusion. Patients will

receive the cream when they start the chemotherapy treatment. Creams will be either sent directly to the participants' home or sent in advance to the centers and stored there at room temperature (15-25°C) until distributed to participants. The principal investigator will create the Data Notebook for each subject, anonymizing the personal and clinical data in all cases. The type of product to be assigned will be determined by the randomization procedure.

Subjects taking part in the study should apply a sufficient amount of cream to their hands once a day for the duration of their chemotherapy treatment. Those subjects who develop skin sensitivity or peripheral neuropathy should undergo the following procedures:

1. Increase the frequency of use of the cream to twice a day in all affected areas.
2. Once the chemotherapy treatment is finished: evaluation of the degree of skin satisfaction by means of a questionnaire that assesses the Dermatology Life Quality Index [DLQI] (Annex II) and the degree of satisfaction with the cream (Annex IV). Evaluation of the discomfort generated by peripheral neuropathy through a follow-up questionnaire (Annex III). Measurement of skin sensitivity using Von Frey hairs for patients who voluntarily wish to do so. These procedures will be carried out by the study collaborators of each center. In case of need, Prospera Biotech team could also contribute to make the follow-up (questionnaires) telematically.

The study procedures are included in section 8.2.

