8.2. Collection of variables

The main variable, degree of skin satisfaction/comfort, will be evaluated using the DLQI^{12, 13} questionnaire available in ANNEX II.

Mechanical sensitivity will be assessed by means of the Von Frey filament test in patients who voluntarily want to undergo it. The pain threshold and mechanical allodynia of patients with post-chemotherapy polyneuropathy will be measured before starting the study and once the chemotherapy treatment is over, expressing the threshold in the minimum number of pressure units that trigger pain in patients with the corresponding filament. of Von Frey approved.

The follow-up of the patients will be carried out through the usual oncological control during treatment. If the patients develop sensory or skin discomfort during this period, at the end of the treatment a check-up will be carried out using the following questionnaires:

- Follow-up of discomfort sensations available in a questionnaire derived from the Leonard Scale (ANNEX III).
- Degree of skin satisfaction by means of the Dermatology Life Quality Index [DLQI] (Annex II).
- Degree of satisfaction with the cream (Annex IV).

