ANNEX IV: SATISFACTION QUESTIONNAIRE

Title: Study for the evaluation of the degree of skin satisfaction of cosmetic creams PB-011 and PB-012 for sensitive skin in oncological patients affected by a palmoplantar polyneuropathy secondary to taxanes.

Principal Investigator: [name]

Reference: 20PB-02

1. Has applying the cream to your hands and/or feet caused you any discomfort?

Nothin									Many
1	2	3	4	5	6	7	8	9	10

2. Has the application of the cream to your hands and/or feet generated any kind of skin reaction?

Nothin									Many
1	2	3	4	5	6	7	8	9	10

3. How would you define your degree of satisfaction with the cream?

Nada									Mucho
1	2	3	4	5	6	7	8	9	10

If, sensorial discomfort or CIPN have appeared during the chemotherapy treatment please answer also:

1. When you apply the cream to your hands and/or feet, do you feel any relief from any of the sensations that bother you?

YES	NO
-----	----

2. Has the application of the cream generated comfort in your skin sensitivity on the hands

and/or feet?

Nothing										A lot
1	2	3	4	5	6	7	8	9	10	

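### Section 12 tests change from baseline in the main variable, but sections 7.2 and 8.2 schedule no baseline DLQI or Annex III, and Annex IV cannot have one

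*Combined protocol and SAP*

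**What the plan says.** Section 12 makes a general promise: "For all the parameters to be measured (both clinical variables and responses to questionnaires) there will be a baseline measurement". The same sentence gives the timing and use of that measurement: "there will be a baseline measurement taken before the start of the protocol that will serve as a control measurement". It then says of the main variable: "The change in the main variable (degree of satisfaction) will be analyzed" "using the paired Student's T test". For the others: "The change in the secondary variables will be studied according to their nature". Section 8.1 defines the main variable as the DLQI. Its secondary variables are the voluntary Von Frey test and a brief questionnaire on discomfort sensations (Annex III). Annex IV is not listed there.

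The procedure sections set the timing. Section 7.2, in a list for subjects who develop skin sensitivity or neuropathy, has: "Once the chemotherapy treatment is finished: evaluation of the degree of skin satisfaction by means of a questionnaire", and names the DLQI, Annex III and Annex IV. Section 8.2 says that if discomfort develops during treatment, "at the end of the treatment a check-up will be carried out using the following questionnaires", and lists the same three. Section 8.2 also places the Von Frey test both before the study and after chemotherapy. The last paragraph of section 3 has skin satisfaction assessed by questionnaire every two weeks, but only where there is discomfort.

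Annex IV asks about the effects of applying the cream and, in its third item, "How would you define your degree of satisfaction with the cream", on a 1 to 10 scale.

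**The concern.** A paired test needs two values from the same patient. Section 12 assumes that both exist for the main variable, while the sections a centre would work from ask for only the second. If centres follow 7.2 and 8.2, the only test named for the main variable cannot be run.

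The loss would be permanent. The patients whose DLQI is collected at the end are identified by what happens during chemotherapy, so a baseline cannot be requested once they are known. It has to be taken from everyone at entry or it is gone.

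For Annex IV the problem is one of logic rather than scheduling: nobody can rate a cream they have not yet used.

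**Working it through.** **1. The schedule, instrument by instrument.**

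| Instrument | Role in 8.1 | Pre-study value scheduled in 7.2 or 8.2 | End-of-chemotherapy value |
|---|---|---|---|
| DLQI | Main | None | Only if discomfort developed |
| Annex III | Secondary | None | Only if discomfort developed |
| Von Frey | Secondary | Yes, volunteers (8.2) | Yes, volunteers |
| Annex IV | Not listed | None, and none possible | Listed with the same condition, although the form has three items for all users and two more for those with discomfort |

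The fortnightly schedule in section 3 also begins only with discomfort, so it supplies no baseline.

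**2. Number of pairs.** Pairs are patients with both a pre and a post value. Under 7.2 and 8.2 no patient has a scheduled pre value for the DLQI or Annex III, so the number of pairs is 0, however many end-of-chemotherapy forms come in.

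**3. Why adding a baseline alone is not enough.** Suppose all 60 patients per arm give a baseline DLQI, all stay to the end, and a fraction f develop discomfort and so have the end value. Pairs per arm are 60f. The documents do not give f for this mix of patients, so it is assumed here.

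- f = 0.3: 18 pairs, 42 baselines unpaired
- f = 0.5: 30 pairs, 30 unpaired
- f = 0.8: 48 pairs, 12 unpaired

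The end-of-chemotherapy DLQI has to be taken in the same patients as the baseline.

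**4. What the sample size was built for.** Inputs from section 6.3: difference 2, SD 3, significance level 0.05 (taken as two-sided), power 95%.

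n per arm = 2 × (1.96 + 1.645)² × (3/2)² = 2 × 13.0 × 2.25 = 58.5, so 59. The t-based calculation gives 59.45, so 60. Power at 60 per arm is 95.5% (normal) or 95.2% (t).

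The stated 60 reproduces as a comparison of two independent means, with no baseline and no pre-post correlation. It therefore corresponds to a between-cream comparison, which is the purpose stated in section 4. It does not correspond to the within-patient paired test in section 12.

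**5. What a baseline would add to a between-cream comparison.** Let r be the baseline-to-end correlation, with equal variance at both times. Relative to comparing end values only, the variance is multiplied by 2(1 − r) if change scores are compared, and by 1 − r² if baseline is a covariate.

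- r = 0: 2 for change scores, 1 for the covariate
- r = 0.5: 1 for change scores, 0.75 for the covariate

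These values of r are assumed. With r near 0, comparing change scores would double the variance, whereas the covariate would cost almost nothing and gain nothing. That favours the covariate, but it does not establish how large any gain would be.

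**The case against.** The strongest reply is that section 12 belongs to the same document and itself promises the baseline. The list in 7.2 describes what happens to patients with symptoms, and the list in 8.2 describes the end-of-treatment check-up. Neither says that no earlier DLQI is taken, and the opening of 8.2 names the DLQI with no timing at all. Section 11.1 has all information recorded in the Annex I notebook, which is not shown and may contain a baseline form. This stands as far as it goes: the documents show a contradiction between sections, not a certain loss of data. But 8.2 spells out a pre-study measurement for Von Frey and gives none for the DLQI, so a centre working from it has no instruction to collect one.

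It is also fair to say that section 6 plans an end-of-treatment comparison between groups, which needs no baseline, and that 60 per arm reproduces without one. A reader might infer that the between-cream comparison becomes impossible. It does not. What fails is the only test that section 12 names for the main variable.

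Three other stronger readings are tempting and unsupported:

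- That section 12 analyses change in every questionnaire, Annex IV included. It promises a baseline for all, but analyses change only in the main and secondary variables, and 8.1 does not list Annex IV. Only the baseline sentence reaches it.
- That Annex IV is the scale behind the sample size. Section 6.3 uses 0 to 10, running from very dissatisfied to very satisfied, and offers Von Frey as an alternative. The Annex IV item runs from 1 to 10 with different anchors.
- That a missing baseline costs a known share of precision. The SD of 3 belongs to the satisfaction scale, and the documents give neither an SD nor a correlation for the DLQI.

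**Conclusion.** The contradiction is real and should be resolved before further patients are enrolled. Section 12 requires pre-treatment questionnaires that 7.2, 8.2 and section 3 do not schedule, and its paired test on the main variable depends on them. If centres follow 7.2 and 8.2 and Annex I holds no baseline form, the DLQI has 0 pairs and the gap cannot be filled afterwards. If Annex I does hold one, the sections still disagree and need aligning, but data need not be lost.

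For Annex IV the conclusion does not depend on Annex I: its items presuppose use of the cream, so the baseline sentence is too broad.

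No figure can be put on lost precision. It depends on a DLQI correlation that the documents do not give, and it could be near zero if patients enter without symptoms. The stated sample size is not in dispute here.

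**What to change.** - In 7.2 and 8.2, add the DLQI and Annex III before first application for every randomised patient, and align the schedule in section 3 with them.
- Collect the end-of-chemotherapy DLQI in the same patients, with or without discomfort, so that each baseline has a pair. The comparison among patients with neuropathy described in section 6 remains possible.
- In section 12, exempt Annex IV from the baseline sentence and compare its post-use score between creams.
- In section 12, state the main analysis as the between-cream comparison of end-of-chemotherapy DLQI with baseline DLQI as covariate. Keep the within-arm paired test as descriptive.
- Check that Annex I carries the matching forms.

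The cost is two short questionnaires at enrolment, which section 12 already promises, a DLQI at the end of chemotherapy for patients without discomfort, and an amendment reviewed by the ethics committee under section 11.4. The covariate may bring little precision, but the baseline is needed for any statement about change.

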5.2. Randomization process

The assignment of cosmetic creams PB-011 or PB-012 to patients will be carried out by a simple randomization procedure, using random numbers.

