6. SELECTION OF SUBJECTS

The inclusion of 120 patients who have been diagnosed with cancer in stages I-III and who are going to start chemotherapy treatment is proposed. Once the treatment is finished, the degree of cutaneous comfort will be compared between the patients who have developed peripheral neuropathy in both groups.

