6.3. Expected number of subjects and justification

A total of 120 volunteers diagnosed with any type of cancer, in stages I-III, who are about to start or have received a maximum of 1 dose of chemotherapy treatment will be studied.

Two study populations are contemplated: (i) population that will receive the PB-011 cream; (ii) population that will receive the PB-012 cream. Both populations will apply the cream on their hands once a day. If sensory discomfort or, in the worst case, peripheral neuropathy appear during the chemotherapy treatment period, the application will be increased to twice daily on the affected areas (generally hands and feet).

The number of volunteers for the study is 60 for each population. This value is based on: (i) a difference of 2 points between both populations (PB-011 and PB-012), on a satisfaction scale of

0 to 10 points, with 0 being very dissatisfied and 10 very satisfied, or 2 points on the Von Frey scale; (ii) a variability (standard deviation) of 3 points in each population; (iii) a p-value of statistical significance <0.05 and, (iv) a probability of finding a statistically significant difference for the p-value <0.05 of 95%.

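### Section 12 tests change with a paired t test, which is not the between-cream comparison that 6.3 powers; a between-cream test of change would keep the stated power only under conditions the plan does not give.

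*Combined protocol and SAP*

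**What the plan says.** - **Section 12** promises a baseline for every parameter, taken before the start. It then says: "The change in the main variable (degree of satisfaction) will be analyzed", and names the paired Student t test. It names no two-group test for the main variable. The cream enters only in a closing sentence about assessing the impact of several factors (treatment, diagnosis, age, gender) on that variable.
- **Section 6** describes a between-group comparison after treatment: "Once the treatment is finished, the degree of cutaneous comfort will be compared between the patients who have developed peripheral neuropathy in both groups".
- **Section 6.3** sizes the trial on "a difference of 2 points between both populations (PB-011 and PB-012), on a satisfaction scale of" 0 to 10 (or 2 Von Frey points), "a variability (standard deviation) of 3 points in each population", "a p-value of statistical significance <0.05" and "a probability of finding a statistically significant difference for the p-value <0.05 of 95" per cent. It concludes: "The number of volunteers for the study is 60 for each population". It mentions neither change nor baseline.
- **Section 4** says the purpose is to find which cream satisfies patients more.
- **Sections 8.1 and 8.2** make the DLQI the main variable. Sections 7.2 and 8.2 schedule it at the end of chemotherapy, in patients who developed discomfort. The only pre-study measurement in 8.2 is the voluntary Von Frey test.

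**The concern.** The plan powers one quantity and tests another. A paired t test asks whether scores moved between the start and end of chemotherapy. That movement mixes the effect of chemotherapy with that of the cream, and two such tests, one per arm, do not compare the creams.

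Replacing the paired test with an unpaired test of change would restore the right comparison but could leave a second problem. Subtracting a baseline removes noise when it is strongly related to the end score and adds noise when it is not. Here the baseline precedes cream use, in patients who have had at most one chemotherapy session and have no pre-existing neuropathy. The end score follows chemotherapy, in patients with discomfort. A weak correlation is plausible, although the documents give no figure. At stake is whether the 95% in 6.3 describes the analysis that will be reported.

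**Working it through.** **Inputs from 6.3:** difference 2, SD 3 per arm, significance level 0.05, 60 per arm, power 95%. Sidedness is not stated; two-sided is used because it reproduces the sample size.

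**Assumptions (not in the documents):** baseline-end correlation r, baseline SD s0, and SD 3 read as the end-score SD. Equal arms of 60 are all taken to be evaluable.

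**Step 1. Reproduce 6.3.** For an unpaired two-sample comparison with difference 2 and SD 3, the normal approximation gives 59 per arm for 95% power (49 if one-sided, which does not match). With 60 per arm, power is 95.5% by the normal approximation and 95.2% by the noncentral t. So 6.3 is a two-sided, between-cream calculation in which the analysed quantity has SD 3. The noncentral t is used below.

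**Step 2. SD of a change score.**

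SD(change) = sqrt(s0² + 9 − 6·r·s0)

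This equals 3 when s0² = 6·r·s0, that is, r = s0/6. Above that value change is less variable than the end score; below it, more variable.

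**Step 3. Power of a between-cream test of change, 60 per arm.**

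| Baseline SD | r at which SD(change) = 3 | SD(change) at r = 0 | Power at r = 0 | Power at r = 0.2 |
|---|---|---|---|---|
| 1 | 0.17 | 3.16 | 93.0% | 95.6% |
| 2 | 0.33 | 3.61 | 85.4% | 91.6% |
| 3 | 0.50 | 4.24 | 72.6% | 81.7% |

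With baseline SD 3, power is about 86% at r = 0.3 and 95.2% at r = 0.5. By the normal approximation, 95% power with baseline SD 3 and r = 0 would need 117 per arm.

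**Step 4. Power of the baseline-adjusted end score.** The residual SD is 3·sqrt(1 − r²), whatever the baseline SD. Power is 95.2% at r = 0, 95.9% at 0.2, 96.7% at 0.3 and 98.7% at 0.5. The covariate costs one degree of freedom, which does not alter these figures at this rounding.

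**Step 5. The test actually named.** A paired t test in one arm of 60, for a mean change of 2 with both SDs 3, has power 94.9% at r = 0 and 99.9% at r = 0.5. The s0/6 threshold does not apply to it, but this is power for a within-patient question, not for PB-011 against PB-012.

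**The case against.** The strongest reply is that the power loss depends on inputs the plan never states. Much of that stands.

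- **SD 3 may be the SD of change.** A reader might infer from section 6 that it is the end-score SD, since a level on a 0 to 10 scale is described and no change is mentioned. That is a reasonable inference, but 6.3 does not say so. If SD 3 is the SD of change, a between-cream test of change has 95% power at any correlation.
- **A reader might infer a fixed rule that r must reach 0.5.** That needs equal SDs at both times. A baseline taken before most discomfort arises may vary less than the end score, which lowers the threshold. The 73% figure combines zero correlation with full baseline variance, and the documents support neither input.
- **The 6.3 scale may not be the analysed one.** It uses 0 to 10 satisfaction, whereas the main variable is the DLQI, for which no SD or target difference is given. If satisfaction with the cream (Annex IV) is meant, no score can exist before the cream is used.
- **Adjustment does not by itself secure 95%.** Section 6 compares only patients who developed neuropathy. If, as an assumption, half do, 30 per arm gives about 72% for the end score before any gain from the covariate.
- **The closing sentence of section 12 could accommodate an adjusted model.** It could, but it specifies no model, no contrast between creams and no primary status.

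None of this rescues the paired test as a comparison of the creams, and the uncertainty about SD 3 is itself a reason to state what it describes.

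**Conclusion.** The mismatch between the paired test in section 12 and the between-cream comparison in sections 6 and 6.3 is plain from the text and needs no assumption. The loss of power is conditional. It arises if SD 3 is the end-score SD, the creams are compared on change, and r falls below about baseline SD/6. Under those conditions it ranges from slight (93% with baseline SD 1 and r = 0) to substantial (73% with baseline SD 3 and r = 0). The documents do not support saying that the trial is underpowered, or that the stated 95% is wrong for the calculation 6.3 describes, which reproduces. What they support is that the planned test does not answer the trial's question and that a baseline-adjusted end score answers it without depending on an unknown correlation. This should be corrected before analysis.

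**What to change.** 1. **Section 12.** Replace the paired t test with a linear model of the end-of-chemotherapy main-variable score on cream and baseline score. Report the adjusted PB-011 minus PB-012 difference with its 95% confidence interval. Keep within-patient change as description only. Chemotherapy agent may be added as a covariate, but the point does not rest on it.
2. **Section 6.3.** The sponsor should state from its source which quantity (end score or change) and which scale SD 3 describes, and align that with the DLQI as main variable. It should not simply be declared the end-score SD.
3. **Sections 7.2 and 8.2.** Reconcile them with section 12. Either schedule the DLQI before the start of cream use, or withdraw the promised baseline. Without a baseline neither change nor adjustment is possible, and the unadjusted end score would have to be compared.

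**Cost:** wording in sections 12 and 6.3, with no extra patients. If no baseline DLQI is being collected, there is also one questionnaire per patient at inclusion, which cannot be recovered for patients already under way.
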